7.7.5 Ancillary Objective #1

Functional Patency Rate Through 12-months

Analysis Dataset:

Treated Analysis Set per section **Error! Reference source not found..**

Analysis Method:

Functional patency will be summarized for the Treated population using a Kaplan-Meier curve through at least 12 months. Analyses will include patency/survival probabilities and 95% confidence interval bands through the 12-month visit. The confidence interval will be calculated using a typical transformation of the survival function: $\log(S(t))$. Subjects not completing the study will be censored after their last available visit.

Endpoint Definition:

Functional patency is defined as freedom from access abandonment from time of first two-needle cannulation. An abandoned dialysis access is one that can no longer be used for one or two needle prescribed dialysis because it is unable to provide adequate blood flow and/or is deemed unsafe for the patient, and the associated problem cannot be corrected by any intervention either medical, endovascular or surgical. Access abandonment due to kidney transplant, for example, shall not contribute to the endpoint and date of censoring is the date their access is abandoned. For time-to-event analysis, day 0 is time of first two-needle cannulation and final date is day of event or day of last follow-up.

7.7.6 Ancillary Objective #2

Physiological Maturation Rate at 3-, 6-, and 12-months

Analysis Dataset:

Treated Analysis Set per section **Error! Reference source not found..**

Analysis Method:

Physiological maturation will be summarized at each relevant follow-up visit as the number and percentage of subjects achieving the endpoint along with exact two-sided 95% confidence limits for the percentage, calculated via the Wilson method. The endpoint will be summarized separately at 3, 6 and 12 months.

Endpoint Definition:

Physiological maturation is defined in an access site as access vessel minimum blood flow rate $\geq 500\text{mL/min}$ and minimum diameter $\geq 5\text{mm}$ as measured by duplex ultrasound.

7.7.7 Ancillary Objective #3

Functional Cannulation Success Through 12-months

Analysis Dataset:

Treated Analysis Set per section **Error! Reference source not found..**

Analysis Method:

Functional cannulation success will be summarized for the Treated population using a Kaplan-Meier curve through at least 12 months. Incidence of success will be characterized as $1-S(t)$ where $S(t)$ is the survival function estimated by the Kaplan-Meier method. Analyses will include probabilities and 95% confidence interval bands through the 12-month visit. The confidence interval will be calculated using a typical transformation of the survival function: $\log(S(t))$. Subjects not completing the study will be censored after their last available visit. For time-to-event analysis, day 0 is date of access creation and final date is day 28 of a 28-day window, in the case of an event, or day of last follow-up.

A sensitivity analysis may be performed where a cumulative incidence curve is estimated and death will be accounted for as a competing risk. The cumulative incidence curve will be descriptively compared to the Kaplan-Meier estimate of incidence.

The observed cumulative incidence estimate may be calculated using the “cmprsk” library in R, with code similar to the following:

```
cmpout1 <- cuminc(time,event)
```

The event variable is 0 if censored, 1 if an event occurs and 2 if a death occurs.

Endpoint Definition:

Functional cannulation is defined as the time to achieve successful use of the endovascular AVF, with two-needle access and at least two hours of dialysis through the access, for more than two-thirds of the dialysis sessions over a continuous 28-day period after access creation.

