## 3. Introduction

### 3.1 Background

More than 500,000 Americans are affected by chronic end stage renal disease (ESRD) necessitating dialysis to stay alive. One fifth of all hemodialysis patients will die each year and another 125,000 new patients will begin dialysis during that same period. Worldwide, there are 1.9 million people on hemodialysis.

In 2019, the National Kidney Foundation updated the Kidney Disease Outcomes Quality Initiation (KDOQI) Clinical Practice Guideline for Vascular Access to include a more patient-focused approach to ESRD management. The intent of the newly adopted “Life-Plan” is to provide each patient with an

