### Analysis Methods:

Functional cannulation success will be summarized for the Treated population using a Kaplan-Meier curve through at least 12 months. Analyses will include probabilities and 95% confidence interval bands through the 12-month visit. Subjects not completing the study will be censored after their last available visit.

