7.1 Study Subjects

7.1.1 Disposition of Subjects

A STROBE flow diagram will be used to describe the disposition of study subjects for analysis of the primary objectives.

Ellipsys Vascular Access System Post Market Surveillance Study Statistical Analysis Plan

Revision 2.0

Page 7 of 25

Form

Medtronic

Figure 1 shows an example of a blank STROBE flow diagram. Subject enrollment status will be presented for all enrolled subjects, followed by number of subjects with a procedure attempt, number of subjects with successful access creation and follow-up compliance thereafter. Subject enrollment will also be presented for each site as the number of subjects enrolled, number with procedure attempts, and number with access created.

An access failure occurs when the Ellipsys device is not deployed due to access failure defined as 1) the needle or wire cannot be introduced, or 2) vessel spasm precludes continuing the procedure. Subjects with an access failure may be re-scheduled for another attempt at access or followed through discharge and exited. If the second access attempt is also not successful, these subjects will be considered access failures and followed for safety through clinic discharge. If the second access attempt is more than 30 days after the initial screening, the subject will be re-screened and given a new subject identification number; the new number will be linked to the previous subject identification number in Electronic Data Capture (EDC) to prevent subjects being included twice in the analysis.

Subject visit compliance, and end of study status will be presented for enrolled subjects in whom the procedure has been attempted and the Ellipsys Vascular Access System deployed, whether successful or not. For each study visit, the following information will be tallied: in window visits, out of window visits, early terminations, deaths, and missed visits. Overall follow-up compliance will be reported as number of subjects who had a follow-up visit within or out of window divided by total number of eligible subjects. The number and percentage of subjects who did/did not complete the study will be summarized overall as well as for each reason for withdrawal or early termination.

Follow-up:

Study exit might include the following reasons:

- Study completed
- Subject lost to follow-up
- Subject death
- Subject did not meet inclusion/exclusion criteria
- Subject was not treated with the study device
- Subject did not provide consent

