7.3 Handling of Missing, Unused, and Spurious Data and Dropouts

For all study endpoints that use time-to-event analysis as the primary analysis, patients lost to follow-up or who have died will be treated as censored or as a competing risk for observation of the endpoint. In instances where partial dates are provided, information from the partial date and other dates provided for the patient will be used to determine a plausible range of possible dates, and then the midpoint of that range will be used.

Missing data for primary safety objective #1 may result from a study procedure attempted but not completed, or loss to follow-up or death prior to endpoint assessment. Missing data for secondary and ancillary endpoints may result from clinical assessments unable to be performed due to a remote visit, or unanswered questions on the Subject and Cannulator Satisfaction surveys. Additionally, not all ultrasound measurements of artery and vein diameters and mean flow rates will be available due to normal variations in subject anatomy. These missing values will be excluded from summaries and analyses. In general, imputation of missing data will not be performed for descriptive statistics.

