7.7 Evaluation of Objectives

7.7.1 Primary Effectiveness Objective

Cumulative Patency through 12 months post AVF creation

Analysis Dataset:

Treated Analysis Set per section **Error! Reference source not found..**

Analysis Method:

Cumulative patency will be summarized for the Treated population using a Kaplan-Meier curve through at least 12 months. Analyses will include patency/survival probabilities and 95% confidence interval bands through the 12-month visit. The confidence interval will be calculated using a typical transformation of the survival function: $\log(S(t))$. Subjects not completing the study will be censored after their last available visit. A sensitivity analysis shall be performed where a cumulative incidence curve is estimated and death will be accounted for as a competing risk. The cumulative incidence curve will be descriptively compared to $1-S(t)$ where $S(t)$ is the survival function estimated by the Kaplan-Meier method.

The observed cumulative incidence estimate may be calculated using the “cmprsk” library in R, with code similar to the following:

```
cmpout1 <- cuminc(time,event)
```

The event variable is 0 if censored, 1 if an event occurs and 2 if a death occurs. Similar code in SAS is possible using the following:

```
proc lifetest;  
  time T*event(0) / failcode=1;  
run;
```

where T is the time variable, event takes a value of 1 for primary events, a value of 0 as a censored observation indicator, and all other values as competing events.

Endpoint Definition:

Cumulative patency is defined as freedom from access abandonment from time of access creation. An abandoned dialysis access is one that can no longer be used for one or two needle prescribed dialysis because it is unable to provide adequate blood flow and/or is deemed unsafe for the patient, and the associated problem cannot be corrected by any intervention either medical, endovascular or surgical. Access abandonment due to kidney transplant, for example, shall not contribute to the endpoint and date of censoring is the date their access is abandoned. For time-to-event analysis, day 0 is time of

access creation and final date is day of event or day of last follow-up. The definition of cumulative patency is derived from reporting standards by Sidawy, et al and Shenoy, et al [1,2].

Additional Analysis:

- Cumulative patency post- surgical or endovascular intervention

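### SAP 7.7.7 reports functional cannulation success as 1 minus Kaplan-Meier with deaths censored and leaves the competing-risk curve optional, so the proportion of treated subjects who succeed is overstated

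*SAP*

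**What the plan says.** SAP 7.7.7 (Ancillary Objective #3) defines the main estimate: "Incidence of success will be characterized as $1-S(t)$ where $S(t)$ is the survival function estimated by the Kaplan-Meier method". Its censoring rule is "Subjects not completing the study will be censored after their last available visit". The section does not name death in that rule. Two things place deaths under it. SAP 7.1.1 lists "Subject death" among the reasons for study exit, separately from completion. And within 7.7.7 death has its own event code only in the cumulative incidence analysis, which is optional: "A sensitivity analysis may be performed where a cumulative incidence curve is estimated and death will be accounted for as a competing risk".

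The general rule in SAP 7.3 does not settle the matter, since it says "patients lost to follow-up or who have died will be treated as censored or as a competing risk for observation of the endpoint".

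For cumulative patency, SAP 7.7.1 is firmer: "A sensitivity analysis shall be performed where a cumulative incidence curve is estimated". SAP 7.7.2 (primary patency), 7.7.3 (assisted primary patency) and 7.8.2 (study-related SAEs) are equally binding. Protocol 13.4.3 gives Kaplan-Meier alone for cannulation success: "Functional cannulation success will be summarized for the Treated population using a Kaplan-Meier curve through at least 12 months".

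On mortality, the only figure is in Protocol 3.1: "One fifth of all hemodialysis patients will die each year".

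**The concern.** The event here is a success that a subject must be alive to achieve. Kaplan-Meier treats a censored subject as someone who would go on to succeed at the same rate as those still under observation. That suits a subject who moves away. It does not suit one who has died, whose chance of later success is zero. The method in effect passes the dead subject's weight to the survivors, some of whom then succeed.

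Most readers will take a 12-month success figure as the share of treated subjects who reached usable two-needle access. 1-KM does not estimate that share. It answers a hypothetical question: what proportion would have succeeded had nobody died. If the optional analysis is left out, a report could follow the SAP to the letter and give only the higher number.

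**Working it through.** **The plan's own figure.** The plan gives no expected cannulation success rate, so there is none to reproduce. Its one computed figure is enrollment: 100/0.75 = 133.3, rounded up to 134, which agrees with SAP 6 and Protocol 13.5. It is used below only to turn percentages into subjects.

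**Inputs.**
- Estimator and censoring rule: SAP 7.7.7.
- Earliest success: about day 28, because SAP 7.7.7 dates the event to the last day of a 28-day window. So s = 28/365 = 0.0767 years.
- 12-month mortality d: assumed 5, 10, 20 and 25%. The 20% is the background figure in Protocol 3.1.
- 12-month 1-KM success p: assumed 50 to 90%.

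**Direction.** With death as the competing event, 1-KM is never below the cumulative incidence computed from the same data. It is strictly above it once a death before success is followed by an observed success. This needs no assumed rate.

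**Size, simplest form** (constant hazards from day 0, time in years). Let a = -ln(1-p) and b = -ln(1-d). Then

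CIF = a/(a+b) × (1 - exp(-(a+b))).

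For p = 0.70 and d = 0.20: a = 1.204, b = 0.223, a+b = 1.427. CIF = 0.844 × (1 - 0.240) = 0.641. The excess is 70.0 - 64.1 = 5.9 points.

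**Size with no success before day 28.** The success hazard becomes a' = a/(1-s) = 1.204/0.923 = 1.304, and

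CIF = exp(-bs) × a'/(a'+b) × (1 - exp(-(a'+b)(1-s))).

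This gives 0.983 × 0.854 × 0.756 = 0.634. The excess is 6.6 points. If all 134 enrolled subjects were treated, that is 0.066 × 134 = 8.8, or about 9 subjects.

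At d = 20% the day-28 form gives:

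| 1-KM | Cumulative incidence | Excess (points) |
|---|---|---|
| 50% | 44.9% | 5.1 |
| 60% | 54.1% | 5.9 |
| 70% | 63.4% | 6.6 |
| 80% | 73.0% | 7.0 |
| 90% | 82.9% | 7.1 |

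**Sensitivity to mortality and timing.** The excess in points as 1-KM runs from 50 to 90% is below. In the early-success variant, the waiting time after day 28 has a median of three months among those who ever succeed.

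| 12-month mortality | Constant hazard from day 28 | Early successes |
|---|---|---|
| 5% | 1.2 to 1.7 | 0.9 to 1.6 |
| 10% | 2.5 to 3.5 | 1.8 to 3.3 |
| 20% | 5.1 to 7.1 | 3.8 to 6.8 |
| 25% | 6.4 to 9.0 | 4.8 to 8.7 |

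**Simulation check.** With 134 subjects, p = 0.70, d = 0.20, 4,000 runs and deaths censored on the day of death, mean 1-KM was 70.1% and the mean share who actually succeeded was 63.5%. The mean gap was 6.6 points, with a 95% range across runs of 3.6 to 10.2.

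**The case against.** The best defence is that 1-KM is a legitimate answer to a no-death question, and that the plan uses Kaplan-Meier as the main display even for primary effectiveness, with cumulative incidence as the sensitivity analysis. SAP 7.2 adds a general promise of cumulative incidence curves where competing-risk adjustment is needed, and 7.7.7 already supplies the coding and a commitment to compare the two curves. On this view only one modal verb is at issue.

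Much of that stands. No method is missing, and 1-KM may stay in the report. But SAP 7.2 does not say when adjustment is needed, and a general line does not override an explicit *may* in the endpoint's own section.

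The size is also fairly challenged. The one-in-five mortality describes all hemodialysis patients. This study caps age at 80 and requires a life expectancy of at least one year (Protocol 8.3), so its mortality may be lower. At 5% mortality the excess is under 2 points.

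Two stronger readings are tempting, and the documents do not support them.

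- *The check was made optional because the bias favours the device.* Functional patency (SAP 7.7.5), also ancillary, has no competing-risk analysis at all, and there censoring deaths overstates abandonment, which works against the device. The pattern fits endpoint tier.
- *Abandonment and transplant before success are also censored, so the gap is much larger.* With a further 10 to 30% a year censored on top of 20% mortality, the excess would be about 7 to 17 points. But the rule that censors at transplant-related abandonment is written for cumulative and functional patency (SAP 7.7.1 and 7.7.5). It is absent from 7.7.7, and neither event is a listed exit reason in SAP 7.1.1. As 7.7.7 reads, such a subject who stays in follow-up remains at risk as a non-success, which does not inflate 1-KM.

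**Conclusion.** The point holds for death. As written, SAP 7.7.7 yields a figure that cannot be below the actual proportion of treated subjects achieving success and will usually be above it, and it does not require the analysis that would show the difference. That deaths are censored in the main analysis is inferred from the exit reasons and the event coding; 7.7.7 does not state it outright.

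The direction is certain; the size is conditional. It is about 1 to 9 points over the assumed ranges. At 70% success and 20% mortality it is 5.9 to 6.6 points under constant hazards and 5.3 if successes come early. A reader might take 6 to 7 points as this study's expected bias, but the documents give no success rate and no planning mortality for this cohort.

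The weight is moderate. The endpoint is ancillary and descriptive, and no hypothesis test, threshold, sample size or primary result depends on it.

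**What to change.** In SAP 7.7.7:

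1. Change *may* to *shall* for the cumulative incidence analysis.
2. Report the cumulative incidence function, with death as a competing event, as the estimate of the proportion achieving success, and show 1-KM beside it. The `cuminc` call and event codes are already in the section.
3. State in one sentence that subjects whose access is abandoned, or who receive a transplant, before success either remain in the risk set as non-successes, as the section now reads, or are coded as competing events. They should not be censored.

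Protocol 13 leaves further detail to the SAP, so no protocol amendment is needed for this alone. Protocol 13.4.3 can be aligned at the next revision.

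The cost is a SAP revision and one more curve. Handling death as a competing event needs no new data. The downside for the sponsor is an ancillary success figure that becomes a few points less favourable.

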7.7.8 Ancillary Objective #5

Subject Satisfaction using the Vascular Access Questionnaire (VAQ) at 6 Months

Analysis Dataset:

Treated Analysis Set per section **Error! Reference source not found..**

Analysis Method:

The VAQ will be summarized for subjects in the Treated population whose primary access is the study AVF. Summaries will present the number and percentage of subjects not bothered by any symptoms and the number and percentage of subjects at least moderately bothered by each symptom. Descriptive statistics for the overall VAQ score will be provided.

Endpoint Definition:

Subject satisfaction with the AVF is assessed at the 6-month visit using the Vascular Access Questionnaire (VAQ), a series of 17 questions measuring how much subjects are bothered by problems related to their primary vascular access. Responses range from 0 (Not at all) to 4 (Extremely) and the 17 items are summed to produce a score. The VAQ summary score ranges from 0 to 68 with a higher value indicating that the subject has a more negative view of their vascular access.

7.7.9 Ancillary Objective #6

Nurse-Cannulator Satisfaction at 3-, 6-, and 12-months

Analysis Dataset:

Treated Analysis Set per section **Error! Reference source not found..**

Analysis Method:

Baseline cannulator training will be summarized using the responses from the first study AVF cannulated by each cannulator. Cannulator experience with the study AVF will be presented for the Treated population at each timepoint, summarizing each question descriptively. Missing responses will not be included.

Endpoint Definition:

Subjective and objective parameters will be assessed including fistula characteristics, cannulator training, skills and experience cannulating this type of fistula. Cannulator training and experience cannulating the study AVF is assessed at approximately 3, 6, and 12 months post AVF creation. If subject has not started receiving dialysis through the study AVF at the time of the scheduled follow-up visit, the Cannulator Satisfaction Survey will not be completed.

7.8 Safety Evaluation

In addition to the safety objectives outlined below, a table compiling all observed device deficiencies that could have led to a serious adverse device effect will be provided. An enumeration of deaths will also be provided.

7.8.1 Primary Safety Objective #1

*Early Occlusion***Analysis Dataset:**

Safety Analysis Set per section **Error! Reference source not found..**

Analysis Method:

Early occlusion will be summarized by presenting the number, percentage, and two-sided 95% CI for the percentage of subjects with early occlusion. Early occlusion will be presented overall and separately by type and location of the occlusion.

Endpoint Definition:

Early occlusion is defined as the percentage of subjects with total occlusion within 7 days (≤ 7) of the AVF creation procedure. These events will be based on the adjudication by an independent CEC. The percentage is calculated where the numerator is the number of patients with total occlusion within 7 days of the AVF creation procedure and the denominator is the number of patients in the Safety Analysis set.

Additional Analysis:

- To assess the short-term safety of the AVF creation procedure, early occlusion will be descriptively compared to the pre-market study (DEN170004). Early occlusion will be compared using the percentage and 97.5% CI for each study (CI adjusted for multiple comparisons). If there are differing representations of baseline characteristics between the two studies, they will be adjusted for in the analysis.

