**Additional Analysis:**

To assess the short-term safety of the AVF creation procedure, early occlusion will be descriptively compared to the pre-market study (DEN170004). Early occlusion will be compared using the percentage and 97.5% CI for each study (CI adjusted for multiple comparisons). If there are differing representations of baseline characteristics between the two studies, they will be adjusted for in the analysis.

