7.2 General Methodology

For continuous variables, the number of observations, mean, standard deviation (SD), median, minimum, and maximum will be calculated, unless otherwise stated. For categorical variables, frequencies and percentages will be calculated. Exact binomial confidence limits will be calculated based on Wilson-score methods.

Survival analysis will also be performed for time-to-event endpoints using the Kaplan-Meier method. In cases where adjustment for competing risks is necessary, cumulative incidence curves will also be provided.

To assess the continued safety of the AVF creation procedure post-market, a subset of study endpoints will be descriptively compared to the pre-market study (DEN170004) results where possible. Comparisons will be performed using the Safety population for each study.

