7.4 Adjustments for Multiple Comparisons

In general, although this post-market study has multiple primary endpoints, they are not hypothesis-driven and therefore their results will be presented descriptively with no adjustments for multiple comparisons. For comparisons between pre-market results and post-market results, however, these comparisons will account for multiple comparisons. Two comparisons between the pre-market study (DEN170004) and the post-market study are anticipated, for Primary Safety Objective #1, and components of Secondary Objective #4. A Bonferroni adjustment to the alpha-level to determine the quantile for the confidence intervals (CIs) in those analysis will be performed. Thus, confidence intervals for these comparisons will be based on 97.5% CIs rather than 95% CIs.

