7.8.3 Secondary Objective #4

Overall patient safety

Analysis Dataset:

Safety Analysis Set per section **Error! Reference source not found..**

Analysis Method:

Study-related AEs occurring during the study will be presented for the Safety population cumulatively and for each of the following study intervals:

Peri-operative: within 7 days (≤ 7 days) of the AVF creation procedure

Post-operative: 8 days to 3 months after the AVF creation procedure

Follow-up: more than 3 months after the AVF creation procedure

AEs will be summarized as the number of events as well as the number and percentage of subjects experiencing one or more of the following event types:

- Any study-related AE:
 - Cumulative
 - Peri-operative
 - Post-operative
 - Follow-up
- AE related to:
 - study device
 - study procedure
 - intra-procedure (index) or planned balloon angioplasty (PTA) maturation procedures
- Cannulation-related AE
- AE resulting from or related to a secondary procedure
- SAE
- UADE
- Stenosis

SAE incidence will be summarized by system organ class and event as the number of events as well as the number and percentage of subjects experiencing each event. The above summaries will be presented cumulatively and for each study interval. For the four different study intervals, subjects are included in the denominator of percentage calculations if their follow-up has extended at least to the beginning of that study time interval. Non-SAE will be presented in manner similar to SAE.

Endpoint Definition:

All adverse events related to the device, procedure, secondary procedures to maintain or re-establish patency, or any serious adverse event shall be reported. An independent CEC will assess and adjudicate any potential relationship to the device and/or procedures per the criteria set in the CEC charter. Stenosis events will be reported based on the MedDRA terms AVF site stenosis or AVF occlusion.

Additional Analysis:

- To assess the safety of the AVF creation procedure, rates for SAEs, UADEs, and procedure-related AEs will be descriptively compared to the pre-market study (DEN170004) results by presenting the rate and 97.5% CI for each study (CI adjusted for multiple comparisons). This comparison will be presented for the peri-operative and post-operative study intervals. If there are differing representations of baseline characteristics between the two studies, they will be adjusted for in the analysis.

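### The pre-market versus post-market safety comparison shows a separate 97.5% CI for each study; add the risk difference with its own CI, and specify the baseline adjustment already promised.

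*SAP*

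**What the plan says.** For early occlusion, SAP 7.8.1 (Additional Analysis) states: "Early occlusion will be compared using the percentage and 97.5% CI for each study". Protocol 13.2.1 has the same sentence. SAP 7.8.3 and Protocol 13.3.4 use the same device for SAEs, UADEs and procedure-related AEs, in the peri-operative and post-operative intervals.

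SAP 7.4 treats these as comparisons that need a multiplicity correction: "Two comparisons between the pre-market study (DEN170004) and the post-market study are anticipated", so "confidence intervals for these comparisons will be based on 97.5% CIs rather than 95% CIs". The method given in SAP 7.2 for a proportion is the Wilson score interval: "Exact binomial confidence limits will be calculated based on Wilson-score methods".

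On confounding, SAP 7.8.1 promises: "If there are differing representations of baseline characteristics between the two studies, they will be adjusted for in the analysis". SAP 7.8.3 and the two protocol sections say the same. SAP 7.5 is softer: if demographics differ, further analyses or adjustments may be needed. Neither document gives an adjustment method, a covariate list or a rule for deciding that the studies differ, and neither says whether subject-level pre-market data are available.

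**The concern.** The quantity of interest in a comparison is the difference, and the plan never estimates it. It gives two one-sample intervals and corrects their level for multiplicity, but that correction controls error for a contrast, and no contrast is reported. A reader given two intervals will often look at whether they overlap, and non-overlap of two 97.5% intervals is a much stricter standard than 2.5%. A moderate worsening in patients of newly trained providers could then be read as no difference.

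The baseline adjustment has a related gap. A Wilson interval on a raw percentage takes no covariates, so the method named does not deliver the adjustment promised. Whether and how to adjust would be settled after the imbalance has been seen.

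**Working it through.** **Inputs from the documents.** Two comparisons (SAP 7.4). Post-market n = 134 enrolled (SAP 6); the Safety population may be slightly smaller because access failures are excluded. Wilson intervals (SAP 7.2). The 97.5% CI is taken as two-sided, because the main early-occlusion interval is a "two-sided 95% CI for the percentage of subjects with early occlusion".

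**Assumed, not in the documents.** Pre-market n = 100, range 80 to 150; pre-market rate 5%, with 10% as a second case.

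**1. The plan's level reproduces.** 1 − 0.05/2 = 0.975. The critical value is z = 2.2414.

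**2. Level implied by reading overlap.** With equal true rates, each SE is proportional to 1/√n. Two intervals fail to overlap when |difference| > 2.2414 × (SE₁ + SE₀). In units of the SE of the difference this is 2.2414 × k, where k = (SE₁ + SE₀)/√(SE₁² + SE₀²).

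For n₀ = 100: 1/√134 = 0.0864 and 1/√100 = 0.1000, so k = 0.1864/0.1321 = 1.410, the threshold is 3.161 and the two-sided level is 0.0016.

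| Pre-market n | k | Threshold z | Two-sided level |
|---|---|---|---|
| 80 | 1.403 | 3.144 | 0.0017 |
| 100 | 1.410 | 3.161 | 0.0016 |
| 150 | 1.414 | 3.169 | 0.0015 |

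**3. Chance of showing a true rise.** This is an exact binomial enumeration over all pairs of counts. Rule A: the two 97.5% Wilson intervals do not overlap. Rule B: the 97.5% Newcombe interval for the difference excludes zero. With d = p₁ − p₀ and Wilson limits l and u, the Newcombe limits are d − √[(p₁ − l₁)² + (u₀ − p₀)²] and d + √[(u₁ − p₁)² + (p₀ − l₀)²].

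| True rates, pre to post | A, n₀ = 100 (80 to 150) | B, n₀ = 100 (80 to 150) |
|---|---|---|
| 5% to 15% | 23% (16 to 36%) | 58% (50 to 73%) |
| 5% to 10% | 3% (2 to 5%) | 16% (12 to 25%) |
| 10% to 25% | 41% (34 to 57%) | 77% (69 to 87%) |

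**4. Rule B does not over-call.** With equal rates of 5% or 10%, it excludes zero 1.4 to 2.2% of the time over the same sizes, below the nominal 2.5%. Rule A does so 0.05 to 0.13% of the time.

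**5. A worked case.** Take 32/134 (23.9%) post-market and an assumed 10/100 pre-market. The separate intervals are 16.7 to 33.0% and 5.1 to 18.7%, which overlap. The difference is 13.9 points, with limits 13.9 − 11.3 and 13.9 + 10.3: about +2.5 to +24.2 points. The same data and level leave opposite impressions.

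**The case against.** The strongest reply is that this is an additional, descriptive analysis. The primary analysis of early occlusion is the single-study rate with a 95% CI, SAP 7.4 says the primary endpoints are not hypothesis-driven, and no overlap rule appears anywhere. The 0.0016 therefore belongs to a reading the plan does not prescribe. That stands: the figures describe what happens if a reader uses overlap, not an error rate the plan commits to. Both percentages are also shown, so anyone with the pre-market counts can compute a crude difference.

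A reader might infer that the plan hides real safety differences, or that separate intervals cannot carry a baseline adjustment. The documents support neither. Directly standardised or weighted rates, each with its own interval, would be an adjusted presentation; the gap is that no such method is specified. Nor do the per-study intervals need to be dropped, since they are useful in surveillance.

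Two further limits are fair. With this sample even the difference interval is a weak detector of a doubling from 5% to 10%. And a mandatory propensity-weighted analysis would assume subject-level pre-market data, which the documents do not confirm: SAP 7.2 plans the comparison only where possible. It could also fail for UADEs. Protocol 10.4 reports no unanticipated adverse events pre-market; if that means zero UADEs, weighting those subjects still returns zero, with no usable variance.

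What remains is that a descriptive comparison should still estimate the quantity compared.

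**Conclusion.** The point holds as a low-cost improvement. The plan corrects the level of its between-study comparisons but never estimates a between-study difference, and it promises a baseline adjustment without a method, in terms that differ between SAP 7.5 and SAP 7.8.1/7.8.3.

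If overlap is used to judge, the effective level is about one sixteenth of the intended one (0.0016/0.025 = 0.064). For a tripling from 5%, the chance of the change showing is less than half of what the difference interval would give. The pre-market size and rate are assumptions, so the percentages are illustrative. The direction is not: k exceeds 1 for any two positive standard errors, so non-overlap is always the stricter standard. The count of two comparisons is taken from SAP 7.4 as it stands.

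**What to change.** In SAP 7.8.1 and 7.8.3, and Protocol 13.2.1 and 13.3.4:

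1. Keep the rate and interval for each study. Add the post-minus-pre risk difference with a Newcombe or Miettinen-Nurminen CI at the multiplicity-adjusted level, for early occlusion and for the SAE, UADE and procedure-related AE rates. For the AE rates, use the percentage of subjects with at least one event, on the interval denominators of SAP 7.8.3. State that overlap of the separate intervals is not to be read as absence of a difference.
2. Make SAP 7.5 agree with 7.8.1 and 7.8.3 on whether adjustment is firm or conditional. If it is conditional, state the trigger.
3. Prespecify one adjusted difference for early occlusion and the more frequent event types. Use a small covariate set from those listed in Protocol 13.1 (age, gender, body mass index, diabetes, hypertension), because events will be few, and a variance suited to weighted estimates. The intervals in item 1 are for unweighted proportions.
4. Name a fallback if subject-level pre-market data are unavailable: reweight the post-market subjects to the aggregate pre-market baseline summaries.
5. For very rare events such as UADEs, report the crude difference only.

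Item 1 costs a few lines of code and needs only the counts behind the planned percentages. Items 2 and 5 are wording. The cost of items 3 and 4 depends on which pre-market data the sponsor holds, which the documents do not say.
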